**Visit 6- Focus Group Visit (usually 1-3 weeks after the final follow-up):**

All participants be invited to participate in a focus group discussion. The discussion sessions, lasting 1 hour, will explore the acceptability of and satisfaction with the PrEPAID programme, components that were useful or not (in terms of helping them with physical activity), and participants' suggestions for changes. Each focus group, will consist of 4-6 participants, and will be facilitated by an independent investigator.

The number of focus groups to be conducted will be determined by data saturation and the sessions will be audio-recorded and will be transcribed verbatim.

Focus Group Visit (90 mins)	Time (mins)	Responsible
Introduction	15	RN + Independent researcher
Focus group interview	60	
Debrief and discharge	15	
If participant is exiting the study at this point:		
1. TENS feedback questionnaire		

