Post-Intervention (70 mins)	
a. Complete questionnaires:
 
 
1. Generic quality of life questionnaire (SF-36)
 
2. Intermittent Claudication Questionnaire (ICQ)
 
3. Visual Analogue Scale (VAS)
 
4. Geriatric Depression Scale (Short Form) (GDS-SF)
 
5. Pain Self-Efficacy Questionnaire (PSEQ)
 
6. Illness Perception Questionnaire (IPQ)
 
 
b. If participant is exiting the study at this point:
 
 
7. TENS feedback questionnaire
 
 
c. Questionnaire on adverse events of interest
	20	UA/JB
	Treadmill protocol • MPQ (5 minutes post-treadmill protocol)	20	
	Fitting of ActivPAL to participants and instruction for use	20	
	Taking of blood sample	10	
Follow-up (70 mins)	
Complete questionnaires:
 
 
1. Generic quality of life questionnaire (SF-36)
 
2. Intermittent Claudication Questionnaire (ICQ)
 
3. Visual Analogue Scale (VAS)
 
4. Geriatric Depression Scale (Short Form) (GDS-SF)
 
5. Pain Self-Efficacy Questionnaire (PSEQ)
 
6. Illness Perception Questionnaire (IPQ)
 
 
If participant is exiting the study at this point:
 
 
7. TENS feedback questionnaire
 
 
Treadmill protocol • MPQ (5 minutes post-treadmill protocol)
	20	UA/JB
	Fitting of ActivPAL to participants and instruction for use	20	
	Taking of blood sample	10	
Focus Group (90 mins)	Introduction Focus group interview	15 60	RN + Independent

	Debrief and discharge If participant is exiting the study at this point: 1. TENS feedback questionnaire	15	researcher
--	--	----	------------

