### Visit 4- Post Intervention Assessment Visit (end of the 6-week intervention):

Outcome assessments and procedure followed in Visit 1 will be repeated including questionnaires, treadmill protocol, blood sample collection and fitting of activPAL. The treadmill test will be by the investigators who are blinded to the participants group allocation. Participants will be given a prepaid envelope to return activPAL.

Post-Intervention Visit (70 mins)	Time (mins)	Responsible

a. Complete questionnaires:
 
 
1. Generic quality of life questionnaire (SF-36)
 
2. Intermittent Claudication Questionnaire (ICQ)
 
3. Visual Analogue Scale (VAS)
 
4. Geriatric Depression Scale (Short Form) (GDS-SF)
 
5. Pain Self-Efficacy Questionnaire (PSEQ)
 
6. Illness Perception Questionnaire (IPQ)
 
 
b. If participant is exiting the study at this point:
 
 
7. TENS feedback questionnaire
 
 
c. Questionnaire on adverse events of interest
	20	UA/JB
Treadmill protocol • MPQ (5 minutes post-treadmill protocol)	20	
Fitting of ActivPAL to participants and instruction for use	20	
Taking of blood sample	10	

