Measure participant's retention throughout the trial and reasons for withdrawal
Monitor, record, manage and follow-up defined adverse events in all groups
Measure uptake of intervention (log of TENS use and attendance at education) and acceptability of these interventions via a questionnaire
Measure blinding fidelity via TENS feedback questionnaire
Outcome completion rate – number of day activPAL is worn at each outcome time point.

Efficacy outcomes

Measurement will be obtained at baseline, following six weeks intervention and at 3 months follow up

Primary efficacy outcomes

Treadmill assessed Absolute Claudication Distance (ACD) (cm).

Secondary efficacy outcomes will include:

Physical activity capacity secondary outcomes

Treadmill assessed Initial Claudication Distance (ICD), assessed by a treadmill exercise using the Gardner treadmill protocol.¹⁹ Measurement will be obtained at baseline, following six weeks intervention and at 3 months follow.

Daily physical activity. We shall specify 3 days activPAL data at each measure as minimum for including patient activPAL data in the efficacy analysis. However, activPAL were time (number of day worn) will be also be reported as part of the feasibility analysis. For secondary efficacy analysis, activPAL data outcomes: total number of **i**) steps; **ii**) upright events; **iii**) walking events; **iv**) Event-based claudication index (ratio of walking events to upright events) participants undertake in a day.²⁰

PROM secondary outcomes

Disease specific quality of life will be as assessed using the Intermittent Claudication Questionnaire (ICQ).

Generic quality of life via the SF-36;

Pain quality will be recorded using the McGill Pain Questionnaire (MPQ) 5 minutes after every treadmill test.

Average Pain intensity in the past 7 days will be recorded using a Visual Analogue Scale

Illness beliefs and psychosocial determinants of health and behaviour will be recorded using the Illness Perception Questionnaire (IPQ), Geriatric Depression Scale (Short Form) (GDS-SF) and the Pain Self-Efficacy Questionnaire (PSEQ).

Qualitative Experience outcome

Analysis Methods

Feasibility and qualitative data analysis

Descriptive statistics will be used to characterize the groups at baseline and to present the feasibility outcomes.

Outcomes related to experience and perception via focus groups will be analysed by framework analysis.

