To determine the feasibility of conducting a definitive trial, descriptive statistics will be used to report the number and proportion of participants who meet the inclusion criteria, who consented to participating, and who dropped out during the trial. Also descriptive analysis will report compliance with intervention by recording participants' attendance to education session, follow up calls, attendance to TENS training session, (rate of use of TENS) rate of outcome measure completion, and total accelerometer wear time. Specifically, the TENS log (questionnaire) as well as inbuilt record of TENS device usage will both be used to analyse patients utilisation of TENS. Acceptability of TENS will be obtained by TENS feedback questionnaire

Further exploration will be carried out to determine factors that impact on propensity to participate looking at the difference in characteristics between participants and non-participants. If less than 10% of the individuals with PAD/IC in the clinic are eligible to participate, or if less than 10% of eligible patients agreed to participate, then the eligibility criteria and recruitment strategy will be adjusted prior to conducting a definitive trial. Adjustment of the recruitment strategy in a definitive trial will be made comparing the difference in the baseline characteristics between participants and non-participants. Similarly, association between participants' baseline characteristics and trial outcome will also inform decision on adjustment of recruitment strategy and stratification factors in the definitive trial. Data collection for the definitive trial will be adjusted based on the information related to type, quantity of missing data, and the mechanisms by which these data are missing.

The transcripts from the focus group discussions will be analysed using framework analysis. The data gathered from the exit interview will form part of acceptability analysis and be used to adapt the intervention to enhance its acceptability in a definitive trial.

Primary efficacy analysis

Differences in the change in ACD will be analysed and effect scores calculated using Chi-squared tests, Mann-Whitney U or Wilcoxon signed-rank tests as applicable for between and within-group comparisons and log-rank method for pooled samples or sub-strata. Baseline participants' variability will be controlled for using the analysis of co-variance.

Secondary efficacy analysis

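### At Visit 6 the TENS feedback questionnaire, the SAP's source for blinding and TENS acceptability, follows an hour's group discussion of acceptability, so those answers cannot be assumed independent or masked

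*Protocol*

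**What the plan says.** **Source of the results.** SAP Section 6 lists, among the feasibility and acceptability outcomes, "Measure blinding fidelity via TENS feedback questionnaire". Under its analysis methods it adds "Acceptability of TENS will be obtained by TENS feedback questionnaire"; Protocol 8.2 says the same. SAP Table 2 has rows for the acceptability questionnaire and for TENS blinding, by arm and overall. It does not divide them by the visit at which the form was completed.

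**When the form is given.** The Visit 4 table lists it under the condition "b. If participant is exiting the study at this point", and the Visit 5 and Visit 6 tables carry the same condition. SAP Section 3 (Timing of outcome assessments) likewise ties blinding, acceptability and ease of use to study exit. Protocol Section 4 (Interventions) differs: it has blinding assessed when the intervention period ends, by asking participants whether they believed their unit worked properly.

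**Visit 6.** Protocol 4.1 states "All participants be invited to participate in a focus group discussion". It continues: "The discussion sessions, lasting 1 hour, will explore the acceptability of and satisfaction with the PrEPAID programme", and "Each focus group, will consist of 4-6 participants, and will be facilitated by an independent investigator". Data saturation decides how many groups are held. The visit table runs introduction, focus group interview, then debrief. In the Study Schedule the last cell reads "Debrief and discharge If participant is exiting the study at this point: 1. TENS feedback questionnaire", and the Visit 6 table in 4.1 also lists the form last.

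**The concern.** A person who attends a focus group and exits there has no earlier scheduled form. That person fills it in just after an hour spent discussing, with three to five other participants, the acceptability that the form then asks about. The answers may be drawn towards the group's view.

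The blinding item is also exposed. Active TENS is set to an intensity the patient feels strongly, and placebo is set to about 6 mA. Masking rests on telling participants that with some doses they may feel nothing although the unit works. The blinding question asks whether they believed their unit was working, and hearing others describe their devices can change that belief. An answer given afterwards may not show what the participant believed during treatment or at the treadmill tests.

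Acceptability is one of the two research aims, and blinding fidelity is a listed feasibility outcome in a placebo-controlled design. Both would inform the definitive trial.

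**Working it through.** **1. Order within Visit 6.** The table rows are introduction 15, interview 60, debrief and discharge 15. Their sum, 15 + 60 + 15 = 90 minutes, reproduces the stated visit length. No time is left for a form before the interview, and the only place given for it is the debrief cell.

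**2. Who completes the form when.**

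| Exit visit | Form relative to group discussion |
|---|---|
| Visit 4 | Before any discussion |
| Visit 5 | Before any discussion |
| Visit 6 | After a 60-minute discussion |

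Table 2 would combine all three.

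**3. Chance that a group contains both TENS types.** Inputs: 20 per arm and 80 in total (Protocol 8.7), hence 40 active and 40 placebo TENS; group size m of 4 to 6 (Protocol 4.1, Visit 6). Assumption: groups form without regard to TENS type. The documents are silent on composition.

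P(both types) = 1 − 2 × C(40, m) / C(80, m)

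- m = 4: 1 − 2 × 91,390 / 1,581,580 = 0.884
- m = 5: 1 − 2 × 658,008 / 24,040,016 = 0.945
- m = 6: 1 − 2 × 3,838,380 / 300,500,200 = 0.974

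With the planned 20% attrition, 64 remain. Taking 32 of each type, the results are 0.887, 0.947 and 0.976, so the answer hardly depends on attrition.

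This is the chance of a mixed group, not the chance that anyone is unmasked. Group influence on the acceptability answers does not need a mixed group.

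**4. Number of forms affected.** This cannot be computed. Attendance is by invitation, and no number of groups is fixed.

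**The case against.** The strongest reply is that Protocol Section 4 already places the blinding assessment at the end of the intervention, before any focus group. If that were followed, the blinding half of the problem would disappear. It stands as a statement of intent, but the visit tables do not carry it out: Visit 4 offers the form only to those exiting then, and the SAP also says study exit. So a reader should not infer that no earlier blinding assessment was intended; the documents conflict. The acceptability half remains either way.

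Three further replies limit the point, and all three stand:

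- **Unmasking is not shown.** A reader might infer that groups will be mixed and that masking will fail. Mixing is inferred from the open invitation and the lack of any separation rule. The planned topics are acceptability, useful components and suggested changes, not sensation or allocation. Because participants are told that some doses may not be felt, differing sensations do not by themselves identify a placebo.
- **The extent is unknown.** A reader might infer that all the blinding and acceptability data are compromised. Forms from Visit 4 and Visit 5 exits precede any discussion. The Visit 6 table is itself conditional on exit, which leaves open that some attenders completed the form earlier.
- **Efficacy is untouched.** Visit 6 follows the final follow-up, so ACD, activPAL and questionnaire outcomes are not affected. The acceptability results are descriptive, with no formal between-group tests. The documents give no within-group correlation, so no loss of precision can be calculated.

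Group interaction is proper in the focus-group data themselves. That is no reason to collect an individual questionnaire after it.

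**Conclusion.** The point holds for participants whose exit visit is Visit 6. As scheduled, their blinding and acceptability answers come after a group discussion of acceptability. They cannot be assumed independent of one another, or to reflect masking during treatment, and Table 2 would pool them with answers given before any discussion. If groups form without regard to TENS type from 40 active and 40 placebo users, 88% (groups of 4) to 97% (groups of 6) would contain both types. How many participants this reaches is unknown. It bears on two feasibility results, not on efficacy. It is worth correcting because the correction is almost free.

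**What to change.** In the Study Schedule and in the Visit 6 table of Protocol 4.1, move the TENS feedback questionnaire ahead of the introduction. State that any form given at Visit 6 is completed individually and collected before the discussion starts.

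Also reconcile Protocol Section 4 (blinding assessed at the end of the intervention period) with the Study Schedule, the Visit 4 to 6 tables and SAP Section 3 (form given at study exit), so that the blinding item is always answered before any focus group. If it is settled on the end of the intervention, the acceptability items still need the new order at Visit 6.

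The cost is one row moved in two tables and a timing sentence aligned across the Protocol and SAP. No extra visit is needed. The form has no time of its own now, so its minutes can come from the 15 allotted to debrief.

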## 4.2 Study Outcome Measures

### 4.2.1 Outcomes of feasibility study:

1. Measure recruitment rates -reasons for non-eligibility and non-recruitment of eligible patients will be recorded via the study screening log
2. Measure participant's retention throughout the trial and reasons for withdrawal
3. Measure patient reported outcomes proposed for a definitive RCT
4. Monitor, record, manage and follow-up defined adverse events in all groups
5. Measure uptake of intervention (log of TENS use and attendance at education) and acceptability of these interventions via a questionnaire

### 4.2.2 Outcomes to synthesize data from which the sample size of a definitive RCT could be estimated.

For sample size calculation, the **Absolute Claudication Distance (ACD)**, assessed by a treadmill exercise using the Gardner treadmill protocol shall be assessed as the primary outcome.

**Secondary outcomes** will include other patient outcomes including physical activity, PROMs and blood biomarkers.

- A. Physical activity capacity secondary outcomes
  - i. **Initial Claudication Distance (ICD)**, assessed by a treadmill exercise using the Gardner treadmill protocol. Measurement will be obtained at baseline, following six weeks intervention and at 3 months follow.
- B. **Daily physical activity (ActivPAL data outcomes), total number of i) steps; ii) upright events; iii) walking events; iv) Event-based claudication index (ratio of walking events to upright events) participants undertake in a day.**
- C. **PROM secondary outcomes**
  - i. **Disease specific quality of life** will be as assessed using the Intermittent Claudication Questionnaire (ICQ).
  - ii. Generic quality of life via the SF-36;
  - iii. **Pain quality** will be recorded using the McGill Pain Questionnaire (MPQ) 5 minutes after every treadmill test.
  - iv. **Average Pain intensity** in the past 7 days will be recorded using a Visual Analogue Scale
  - v. **Illness beliefs and psychosocial determinants of health and behaviour** will be recorded using the Illness Perception Questionnaire (IPQ), Geriatric Depression Scale (Short Form) (GDS-SF) and the Pain Self-Efficacy Questionnaire (PSEQ).
- D. **Blood biomarkers:** to assess angiogenesis/inflammatory response.

#### 4.3 Laboratory Tests

20mls of blood will be taken from rested subjects at visits **1, 4 and 5**, spun and stored as per the SOP at CRF at QEUH for future analysis of markers of angiogenesis and inflammatory response.

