##### Visit 1- First Assessment Visit:

At the first visit, participants will be assessed for eligibility and those eligible will be requested to consent for further screening. Baseline outcome measurements will be conducted including weight/height/HR/blood pressure, ABPI, Treadmill assessments, questionnaires and taking of blood sample ([name] and/or Research Nurse). Participants will be fitted with the activPAL™ monitor and advised to wear this continuously for seven days. They will be given an instruction on how to use the activPAL, and provided with a sleep diary to complete during the duration of wearing the activPAL.

First Assessment Visit (90 mins)	Time (mins)	Responsible
Review of Inclusion/Exclusion Criteria Obtain Informed Consent	20	RN/UA
Participant demographics 

Gender / Date of birth / Height / Weight / Heart rate / Blood pressure

 Patient history 

Diagnosis of PAD (Date of diagnosis/Type of disease)

Present drug history (Statin/Antiplatelet/Anticoagulants)

Past Medical History (IHD/MI/LVH)

Cardiac risk factors (DM/Family History of IHD,CVA/Smoking: Current, Previous, Non-smoker/Alcohol excess: Current, Previous, Never/Hypercholesterolemia/Hypertension

	20	
Complete questionnaires: 

Generic quality of life questionnaire (SF-36)

Intermittent Claudication Questionnaire (ICQ)

Visual Analogue Scale (VAS)

Geriatric Depression Scale (Short Form) (GDS-SF)

Pain Self-Efficacy Questionnaire (PSEQ)

Illness Perception Questionnaire (IPQ)

	20	
Taking of blood sample	10	
Treadmill protocol 

ABPI assessment

McGill Pain Questionnaire (MPQ) (5 minutes post-treadmill protocol)

	20	
Fitting of ActivPAL to participants and instruction for use	20	

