**Visit 5- Follow-up Assessment Visit (3-months post-intervention):**

All participants recruited within first eight months of recruitment will be invited to return for a 3-month follow-up visit. Outcome assessments and procedure followed in Visits 1 and 4 will be repeated including questionnaires, treadmill protocol, blood sample collection and fitting of activPAL. The treadmill test will be by the investigators who are blinded to the participants group allocation. Participants will be given a prepaid envelope to return activPAL. We shall allow assessment visit window of  $\pm$  2 weeks.

Follow-up Assessment Visit (70 mins)	Time (mins)	Responsible

Complete questionnaires:
 
 
1. Generic quality of life questionnaire (SF-36)
 
2. Intermittent Claudication Questionnaire (ICQ)
 
3. Visual Analogue Scale (VAS)
 
4. Geriatric Depression Scale (Short Form) (GDS-SF)
 
5. Pain Self-Efficacy Questionnaire (PSEQ)
 
6. Illness Perception Questionnaire (IPQ)
 
 
If participant is exiting the study at this point:
 
 
7. TENS feedback questionnaire
 
	20	UA/JB
Treadmill protocol • MPQ (5 minutes post-treadmill protocol)	20	
Fitting of ActivPAL to participants and instruction for use	20	
Taking of blood sample	10	

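### The order of blood draw and treadmill test differs across visits and rest is undefined, so biomarker change may compare pre-exercise with post-exercise samples

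*Protocol*

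**What the plan says.** Protocol section 4.3 sets the sampling condition: "20mls of blood will be taken from rested subjects at visits" 1, 4 and 5. It refers to a facility SOP for spinning and storage, which is not reproduced. Nowhere is rest defined, and no minimum interval after walking is given.

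The order of blood and treadmill is given in several places:

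- **Visit 1 tables** (Study Schedule and section 4.1): questionnaires, blood, treadmill, activPAL fitting.
- **Visit 1 narrative** (section 4.1): "ABPI, Treadmill assessments, questionnaires and taking of blood sample". Blood comes after the treadmill, the reverse of the table below it.
- **Visit 4 narrative**: "Outcome assessments and procedure followed in Visit 1 will be repeated including questionnaires, treadmill protocol, blood sample collection and fitting of activPAL". Blood comes after the treadmill but before the activPAL.
- **Visit 4 tables**: questionnaires, then "Treadmill protocol • MPQ (5 minutes post-treadmill protocol"), then activPAL fitting, then blood.
- **Visit 5**: the narrative says "Outcome assessments and procedure followed in Visits 1 and 4 will be repeated" and names the same sequence as at Visit 4. In the tables the last row is "Taking of blood sample".

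Blood biomarkers are a secondary outcome in Protocol section 4.2.2. Protocol section 8.4 and the SAP's secondary efficacy analysis compare changes in them both within and between groups.

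**The concern.** The quantity to be analysed is a change from baseline, so both ends should be measured in the same physiological state. The treadmill test is not a light task: the protocol glossary defines the absolute claudication distance as a walk continued until it can no longer be tolerated. If the baseline sample precedes that walk and the follow-up sample comes after it, the change contains any acute response to exercise as well as any effect of treatment or time. A single sample per visit cannot separate the two.

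The plan does not ask for the draw time relative to the treadmill to be recorded. A sample taken out of sequence could therefore not be recognised later, when the stored samples are assayed.

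**Working it through.** The plan states no figure to reproduce. The check compares the listings, then works out what they would imply.

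**1. Slot times if the section 4.1 tables are followed literally**

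| Visit | Slots in listed order (min) | Sum | Stated length |
|---|---|---|---|
| 1 | consent 20, history 20, questionnaires 20, blood 10, treadmill 20, activPAL 20 | 110 | 90 |
| 4 and 5 | questionnaires 20, treadmill 20, activPAL 20, blood 10 | 70 | 70 |

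At Visit 1 blood occupies minutes 60 to 70 and the treadmill minutes 70 to 90, so the sample is pre-exercise. At Visits 4 and 5 the treadmill occupies minutes 20 to 40, the activPAL 40 to 60 and blood 60 to 70. Blood then starts 60 − 40 = 20 minutes after the treadmill slot ends. If the pain questionnaire 5 minutes after the test closes that slot, blood starts about 20 + 5 = 25 minutes after walking stops.

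**2. If the narratives are followed instead**

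Blood comes after the treadmill at all three visits. At Visits 4 and 5 it comes straight after the treadmill slot, so about 5 minutes after walking stops on the same assumption. An acute shift of the same size at each visit would then cancel in the change from baseline.

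The two readings give different sampling conditions, and nothing in the documents says which prevails.

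**3. Consequence under the table order**

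Let a be the acute shift in a marker at the placebo-arm walking distance, in SD units, and let k be the extra relative distance walked by the active arm. Assume that the shift is proportional to distance.

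- Error in within-group change, placebo arm: a
- Error in within-group change, active arm: a(1 + k)
- Error in the between-arm difference: a(1 + k) − a = ak

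The documents give no value for a, so 0, 0.2 and 0.5 SD are assumed for illustration. For k, 0 means an equal shift in all arms, 0.1 is an assumption, and 0.4 is the approximate pilot gain for TENS in Protocol section 1.3.

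| a (SD) | Within-group error, placebo arm | Between arms, k = 0 | k = 0.1 | k = 0.4 |
|---|---|---|---|---|
| 0 | 0 | 0 | 0 | 0 |
| 0.2 | 0.2 | 0 | 0.02 | 0.08 |
| 0.5 | 0.5 | 0 | 0.05 | 0.20 |

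The value k = 0.4 is generous. It comes from TENS worn during the treadmill walk, and section 1.3 adds that any gain from daily-life use has not been assessed.

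**The case against.** The strongest reply is that the tables list tasks and are not a running order. No section says otherwise. The Visit 1 slots overrun the stated visit by 20 minutes, and the Visit 1 narrative contradicts its own table. Section 4.3 sets one condition for all three visits, and the Visit 4 and 5 text asks for the Visit 1 procedure to be repeated. On this view the plan already intends comparable samples. This stands as far as it goes: post-exercise sampling at follow-up only is possible, not established. It does not settle the matter, because the Visit 1 procedure to be repeated is itself described in two orders, and the listings for Visits 4 and 5 all place blood after the treadmill.

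Three stronger readings are tempting, and the documents do not support them:

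- A reader might infer that the rest requirement is broken. With rest undefined, a draw about 25 minutes after walking does not demonstrably breach it.
- A reader might infer that every follow-up sample is affected and no baseline sample is. That takes the table order as the actual order, and the Visit 1 narrative points the other way.
- A reader might infer that the randomised comparison is biased. The listed order is the same in all four arms, so a common shift cancels. Only a part that depends on distance walked could remain, and its existence is an assumption.

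It is also fair to say that little rests on this outcome. The SAP mentions biomarkers in its secondary analysis sentence, but not in its outcome definitions or in the shells of Tables 3 to 5. The protocol's amendment summary describes the Visit 5 blood sample as optional.

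**Conclusion.** The inconsistency is real and can be verified from the text. The sequence of blood and treadmill is not fixed, the listings disagree, and the rest condition is undefined. If staff follow the tables, the within-group biomarker change absorbs the whole of any acute exercise effect. The between-arm difference absorbs only the part that varies with distance walked. That would be 0 to 0.20 SD for an acute shift of 0 to 0.5 SD and up to 40% extra distance, under assumed proportionality. The acute effect may be zero, since the documents give neither its size nor its duration.

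Severity is low. Biomarkers are a secondary outcome of a feasibility trial, and the samples are stored for later work. No feasibility outcome, claudication-distance analysis or sample size estimate is touched. The correction is still worth making, because it is nearly free and the sampling conditions cannot be reconstructed afterwards if times are not recorded.

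**What to change.** - Reconcile the Study Schedule, the Visit 1, 4 and 5 tables and narratives in section 4.1, and section 4.3. List blood before the treadmill test at Visits 1, 4 and 5.
- State in section 4.3 one rest condition that applies to all three visits.
- Record the blood draw time and the treadmill start time on the e-CRF.
- Add a line to the SAP's secondary efficacy analysis: flag samples drawn after the treadmill and examine their influence in a sensitivity analysis. Do not exclude them automatically. If visits have run in table order, exclusion would discard all follow-up biomarker data.

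The cost is some reordered table rows, three corrected narratives, a sentence or two in section 4.3 and in the SAP, and two time fields. It adds no visits, no participants and no new clinical procedures.
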